The primary purpose of this study is to evaluate the effects of yoga on: 1) psychological health, specifically measured as stress level, stress coping strategies, depression, anxiety, well-being, life harmony, diet, and sleep quality; and 2) physiological health, specifically measured as blood plasma and serum stress markers (e.g., hormones, inflammation), blood plasma stress-related indicators (i.e., metabolic and cardiovascular function), and non-invasive clinical measures of stress-related indicators (i.e, cardiovascular and autonomic nervous system function) including blood pressure, arterial stiffness (via pulse wave velocity), and heart rate variability (via electrocardiogram), as well as digestive health via gut microbiota fecal sampling. Further, we intend to explore whether any changes in coping strategies (breathing, mindfulness) as a result of yoga practice may correspond to predictable changes in well-being.

Method

Participants

We plan to conduct a randomized controlled field experiment. In order to properly evaluate the effects of the intervention statistically, we will recruit approximately 120 individuals (please see power analysis below). Study participants will be recruited primarily from the ongoing Malmö Offspring Study (MOS; Dnr 2012/594) which takes place at the Clinical Research Unit at Skånes University Hospital in Malmö (Klinisk Forskningsavdelning på Skånes universitetssjukhus i Malmö). MOS is an inter-generational study where all children and grandchildren of individuals in the Malmö Diet and Cancer Cardiovascular Cohort (MDC-CC; n=6103) are invited to participate. The MDC-CC is a population-based study that investigates the epidemiology of carotid artery disease (LU 51-90 and Dnr 2009/633; Melander, et al., 2009, 2012). Individuals participating in MOS who have indicated an experience of chronic stress during the past year will be contacted by the research team. Other individuals visiting the Clinical Research Unit and/or members of the community are also eligible to participate in the study according to the inclusion/exclusion criteria (please see below).

Procedure

1. Telephone and In-Person Recruitment and Screening

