Recruitment will be accomplished in two ways, 1) via telephone, and/or 2) in person. Telephone recruitment will be directed to participants in the Malmö Offspring Study (MOS) as described above. For individuals in MOS indicating a chronic experience of stress within the past year, information letters will be sent (see Appendix 3). Then they will be contacted by a person employed by the research project. During the telephone call, information about

the current yoga study, as described in the information letter in the Appendix 3 and Appendix 4:1 will be given, and the person will be asked if he/she is interested in participating. The telephone interviewer will also ask questions related to the inclusion/exclusion criteria described below. In-person recruitment will be directed to individuals visiting the Clinical Research Unit at Skånes University Hospital in Malmö who indicate high stress to the personnel. They will be orally given the same information as during the telephone interview previously described. Recruitment will take place over an approximate 2-month period.

Inclusion criteria:

1. A score on four items of the Perceived Stress Scale (PSS; Cohen et al., 1983) between 8-16, thereby indicating a current stress experience of at least moderate level (please see Appendix 5:12).
2. Ability to participate in the intervention during the time-period.
3. Comprehensive in Swedish (the intervention will be in Swedish).

Exclusion criteria

1. Ongoing yoga practice or any regular practice of yoga or meditation within the last 6 months.
2. Any known physical limitations that may prevent light physical activity (yoga postures).

When a person qualifies for the study, an appointment will be scheduled for him/her to come to the Clinical Research Unit at Skånes University Hospital in Malmö for the initial tests to be taken (see Measures below). The name of each participant will only be registered on a single master list in combination with a numeric code to ensure participant anonymity (please see Ethical Considerations below for further detail). Numeric codes will be used throughout the remainder of the study to identify participants. Additionally, the master list will provide the randomly generated number indicating which study group he/she is assigned to. Each person will be randomized at the individual level to one of the following conditions:

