At the follow up measurements, after the 5-week yoga practice, the participants will again be invited to the Clinical Research Unit at Skånes University Hospital in Malmö and have the same physiological measures taken as in the the first appointment. They will also fill out the same survey with psychological measures as they did at the first appointment. Breakfast will again be offered following completion of the measures. Finally, participants will be thanked for their participation in the research study.

Required sample size and a priori power analyses

The main statistical analyses will be regression analyses by estimating the models with full-information maximum likelihood (FIML) in AMOS software allowing to perform Intent-To-Treat analyses. The outcome variables will be all study variables calculated as the difference between pre-test and post-test scores.

Mediation models will be tested with the macro PROCESS by Preacher and Hayes (2008) which implements a bootstrapping procedure to create confidence intervals for indirect effects in the mediation model.

G*Power, 3. 1. 7 (Faul, Erdfelder, Lang, & Buchner, 2007) was used to calculate a priori power for analyzing main effects. Assuming that the effect is medium size ($f = 0.25$; see Cohen, 1988), a significance level is of $\alpha = .05$, and the power values of the F tests are .95, a total of $N = 105$ must be recruited.

Ethical Considerations

This research will follow the ethical guidelines regarding informed consent and confidentiality as specified by etikprövningslagen (2003:460). All participants will be informed of the study's aim and method, both orally and in writing, as well as sign an informed consent document prior to participation (see Appendix 4:1-4:2). They will be informed that their participation is completely voluntary and that they can discontinue participation at any time, without giving a reason. Contact information for the project leader will be provided to answer any questions.

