The name of each participant will be registered on a single master list in combination with a numerical code. The list will be kept in a locked closet at the Clinical Research Unit at Skånes University hospital in Malmö, stored apart from other study documents. Numeric codes will be used throughout the research on all study documents to identify participants, in order to preserve confidentiality. Once data have been collected, the list with participants' names will be destroyed, ensuring that the identity of the participants will remain undisclosed. No individual names will ever be included in the data file. All study documents will be kept in locked closets, and contain no person names. The data used to assess the inclusion / exclusion criteria in the study (see above), will not be saved for participants excluded from the study. Any data collected from participants choosing to discontinue the study will be destroyed.

Bio-banking and laboratory analysis: Region Skåne biobank BD53 ([contact]) will be the biobank used in this study to store biological samples (i.e., blood serum and plasma, fecal samples). The biobank utilizes a freezer (-80 degrees) where biological samples are kept frozen until the time of analysis. Samples are not marked with a person's name or social security number, but with a numerical code that can only be connected to the participant (described above). Biological samples will be subsequently analyzed at the Department of Clinical Sciences, Faculty of Medicine, Lund University. The person responsible for bio-banking and laboratory analysis of biological samples is [name], Clinical Research Unit, Department of Clinical Sciences, Skåne University Hospital, Malmö, T: [name].

One possible risk of participating in this research is that individuals may experience some distress in participating in the study measurements. Blood sample collection and glucose tolerance testing require participants to come to their appointment in a fasting state. This

may cause some people to experience hunger and/or fatigue. To minimize discomfort, appointments are made in the early morning and blood collection will be among the first procedures performed. Participants will receive breakfast for free after the study measurements are complete.

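### Destroying the data of participants who withdraw conflicts with the intent-to-treat FIML analysis and can bias the yoga-versus-control contrasts

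*Combined protocol and SAP*

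**What the plan says.** Three places in the combined protocol and SAP bear on this.

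- **Required sample size and a priori power analyses.** The main analyses are regressions estimated by "full-information maximum likelihood (FIML) in AMOS software allowing to perform Intent-To-Treat analyses". On outcomes it says: "The outcome variables will be all study variables calculated as the difference between pre-test and post-test scores". No baseline covariate or auxiliary variable is named.
- **Ethical Considerations.** Participants are told that "they can discontinue participation at any time, without giving a reason". Later in the section: "Any data collected from participants choosing to discontinue the study will be destroyed". The sentence makes no exception for baseline data and does not depend on a request for deletion. The term discontinue is not defined.
- **Procedure, recruitment and screening.** "Each person will be randomized at the individual level to one of the following conditions". Allocation is held separately from the measurements: "Additionally, the master list will provide the randomly generated number indicating which study group he/she is assigned to". That list is itself to be destroyed once data collection ends.

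Nothing in the document reconciles the destruction rule with the intent-to-treat statement.

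**The concern.** Intent-to-treat means that everyone randomised counts in the arm to which they were assigned. FIML can serve that aim for a person without a post-test only if that person's allocation and observed scores are still in the file. The destruction rule removes the scores of everyone who chooses to leave the study.

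Withdrawal could plausibly differ by arm. Two arms are asked to attend ten evening sessions over five weeks, and one of them also has homework. Control attends nothing in that period, and the protocol itself foresees that controls may be unhappy with their assignment. If those who leave differ from those who stay, and differ differently by arm, a contrast among the remaining participants is no longer protected by randomisation. With the baseline data destroyed, nobody can examine whether this happened.

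**Working it through.** **1. The two rules side by side, by type of participant**

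| Participant | Covered by the destruction rule? | Position under the stated analysis |
|---|---|---|
| Stops classes, attends post-test | Not on the natural reading, but discontinue is undefined | Has a difference score; analysed as randomised |
| Misses post-test without choosing to withdraw | No | Record stays, but there is no difference score |
| Actively withdraws before post-test | Yes | Baseline destroyed; cannot be analysed as randomised |

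The conflict lies in the third row. It is a matter of logic and needs no dropout figure.

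**2. Would a retained baseline help under the stated model?** Not by itself. The outcome is post minus pre, which is missing for anyone without a post-test. With no baseline term in the model, such a person adds nothing to the arm contrast. Retention helps the estimate only if the baseline score enters the model. It helps baseline comparisons and sensitivity analyses in any case.

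**3. Illustrative size.** The documents give no dropout rate, so these inputs are assumptions. Let p be the fraction withdrawing in an arm and g the amount, in SD, by which those who leave would have done worse than those who stay.

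Error in the contrast = p(yoga) × g(yoga) − p(control) × g(control)

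- 20% yoga withdrawal, g = 0.5, no control withdrawal: 0.20 × 0.5 = 0.10 SD.
- 30% yoga withdrawal, same g, no control withdrawal: 0.30 × 0.5 = 0.15 SD.
- The same p and g in control: zero.

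For scale, the plan's effect size is given as "Assuming that the effect is medium size ($f = 0.25$; see Cohen, 1988". With three equal arms (an assumption; the allocation ratio is not stated) and two equally effective yoga arms, f = d√2/3. Then d = 0.25 × 3/√2 = 0.53, and 0.10/0.53 is about 19%.

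**4. Does the mechanism matter?** Simulation with assumed inputs: no true effect, 40 per arm, pre-post correlation r = 0.5, dropout about 26% in yoga and 5% in control.

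| Dropout depends on | Completers' change score | Maximum likelihood with retained baselines |
|---|---|---|
| Baseline | about −0.12 SD | about 0.01 SD |
| Unobserved post-test | about 0.13 SD | about 0.19 SD |

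A hand check agrees. If selection on baseline shifts the completers' baseline mean by m, the change-score bias is (r − 1)m; −0.12 corresponds to m = 0.24. If selection on the post-test shifts its mean by s, the change-score bias is (1 − r)s and the baseline-adjusted bias is about (1 − r²)s. With s = 0.26 these are 0.13 and 0.195. The sizes depend on how steeply dropout is assumed to follow the score. The pattern does not.

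In the first row, a baseline-adjusted analysis of completers alone was also nearly unbiased (about 0.01 SD). Part of the protection therefore comes from having baseline in the model.

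**5. The plan's sample size.** This point does not rest on the stated N = 105, and that figure was not reproduced from the stated inputs. A one-way three-group F test at f = 0.25, alpha 0.05 and power 0.95 gives N = 252. Values near 105 appear only with inputs that the plan does not state. That is a separate matter.

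**The case against.** The strongest case on the other side is that the rule is narrow. It concerns people who choose to leave the study, not those who stop attending yoga. The post-testing section invites participants back without making this depend on attendance. People who miss the second visit without withdrawing, or who lack single measures, keep their records. All of this stands, with the caveat that discontinue is undefined and could be applied more widely in practice.

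Several stronger readings are tempting, and the documents do not support them.

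- A reader might infer that the trial becomes a completers-only comparison, or that FIML has no incomplete records to use. The table above shows otherwise.
- A reader might infer that group assignment is destroyed too. Allocation is generated by the study and held on the master list, so it is not clearly among the data covered. Withdrawals by arm may remain countable until that list is destroyed.
- A reader might infer that every between-arm estimate is biased against or in favour of yoga. Neither the rate nor the mechanism is given. Control withdrawals could offset or reverse the error, and the contrast between the two yoga arms may be little affected if their withdrawal is similar.
- A reader might blame the destruction rule for a fall below 105 once dropout passes 12.5% (105/120 = 0.875). That shortfall comes from missing post-tests and would occur with every baseline retained. The plan also states 105 as a number to recruit.

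Finally, the consent and information texts are in appendices that were not available for this review. They may define discontinuation or promise deletion.

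**Conclusion.** The conflict is real for participants who actively withdraw from the study. As written, the plan loses their baseline data irreversibly, so they cannot be analysed as randomised, compared at baseline with those who remain, or carried into sensitivity analyses. These consequences need no assumed dropout rate.

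Bias in the yoga-versus-control contrasts is possible, and its size and direction are unknown. The 0.10 SD figure rests on 20% withdrawal, a 0.5 SD gap and no offsetting loss in control, none of which comes from the documents. Retaining the data is necessary for an intent-to-treat analysis of these people but not sufficient. With difference scores and no baseline term, retained baselines would not inform the arm contrast.

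**What to change.** Replace the destruction sentence and amend the analysis paragraph so that:

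- (a) stopping classes is not treated as leaving the study, and those who stop are still invited to post-testing;
- (b) data collected before withdrawal are kept in coded form and analysed in the randomised group unless the participant asks for deletion. This applies only where the consent given allows it, and the consent text is aligned;
- (c) the number withdrawing is reported by arm, with reasons only if volunteered, which respects the right to leave without explanation. The counts should be recorded before the master list is destroyed;
- (d) the FIML model takes the post-test as outcome with the baseline score in the model, or baseline as an auxiliary variable, so that retained baselines inform the estimate.

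The cost is revised protocol and consent wording and an ethics amendment or notification. Anyone already promised deletion must keep that promise. Bias remains if dropout depends on the unobserved post-test; obtaining post-tests under (a) addresses that most directly.

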- 1) Group 1: Stress education + Yoga (SED_YOGA). Education about stress plus yoga practice, 2 times per week for 5 weeks.
- 2) Group 2: Yoga (YOGA). Yoga practice, 2 times per week for 5 weeks.
- 3) Group 3: Control (CONTROL). Education about stress plus yoga practice, 1 session after the 5-week main study is completed.

2. First Appointment at the Clinical Research Unit (pre-testing)

At the first appointment, participants will be given a detailed information letter to read about the study and his/her participation (please see Appendix 4:1). Participants will also have the opportunity to ask any questions about the study and his/her participation. He/she will then be given the informed consent document to read and sign (please see Appendix 4:2). When informed consent is given, a copy will be provided to the participant, and the study measurements will begin.

Measures

Physiological measures:

Physiological measures will be carried out at the beginning of the appointment in order to capture, in particular, fasting blood samples. The full battery of physiological measures entails:

- 1) Fasting blood sampling (serum and plasma). Blood sampling will be performed via venipuncture which involves extracting venous blood through a small sterile needle and collection in a vacutainer (sterile glass or plastic tube). A total of 3 tubes will be collected for each participant, amounting to a total of 65ml of blood per person. Blood samples will then be sent to a biobank. A biobank is a freezer (-80 degrees) where biological samples are stored (please see Ethical Considerations for further details). Blood analysis will include stress hormones, inflammatory biomarkers, metabolic profiling, cardiometabolic biomarkers, cholesterol, triglycerides, creatinine, catecholamines (noradrenalin and adrenalin), renin, cortisol, and glucose concentration.
- 2) Fasting and 120-minute glucose tolerance test. The glucose tolerance test determines how the body responds to glucose (sugar). After a fasting blood sample is taken (see above procedure), participants will be asked to drink a liquid containing glucose. A second blood sample will be taken 120 minutes later.

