Another possible risk is that some participants may experience discomfort with the venipuncture procedure. To minimize this risk, blood collection will only be performed by licensed medical staff at the Clinical Research Unit, Skånes University hospital.

Fasting and 120-minute glucose tolerance test requires participants to drink a liquid containing glucose (sugar) between their first (fasting) and second (120-minute) blood samples. This may cause some participants to feel nervous or anxious about ingesting a liquid. However, the drink is merely sweet, and there are no known risks from participating in a glucose tolerance test.

An electrocardiogram will be performed by a member of the Clinical Research Unit, which may cause some people to feel nervous or embarrassed about having electrodes attached to their upper torso and limbs. However, the electrical signals that are recorded by the machine in reading the activity of the heart are painless. It only requires the participant to lie down and remain still for a few minutes.

Participants may also experience some anxiety or embarrassment about having to produce a fecal sample. However, this is a normal bodily function that causes no harm. Participants will be given the option of giving the sample while at the hospital or, alternatively, in the privacy of their home (and returning the sample the following day). Staff at the Clinical Research Unit are routinely handling biological samples, so it will not appear as an abnormal process.

Participants will be informed about all abovementioned physiological study procedures during the recruitment and informed consent process. They are free to decline participation in this study for any reason. Participation is completely voluntary.

Participants will receive feedback on their results for all physiological measurements that have clinically accepted parameters. This includes information on blood pressure, plasma glucose & lipids and electrocardiogram results. Participants will not receive feedback on exploratory measures since there are no established clinical parameters. This includes all blood sampling procedures, pulse-wave velocity, heart-rate variability and gut microbiota fecal sampling. This information will be made known in the recruitment and informed consent process.

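### No entry criterion or described screening step asks about diabetes or glucose-lowering treatment, although a fasting glucose tolerance test is planned at both visits and the ethics text denies any known risk

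*Combined protocol and SAP*

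**What the plan says.** **Entry.** The recruitment and screening section of the Procedure lists three inclusion criteria: a score of 8-16 on four Perceived Stress Scale items, availability ("Ability to participate in the intervention during the time-period"), and Swedish. It lists two exclusions: "Ongoing yoga practice or any regular practice of yoga or meditation within the last 6 months", and physical limitations that would rule out the yoga postures.

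**Screening.** Of the call, the plan says: "The telephone interviewer will also ask questions related to the inclusion/exclusion criteria described below". People approached in person at the Unit are given the same information orally.

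**From screening to test.** The next step is: "When a person qualifies for the study, an appointment will be scheduled for him/her to come to the Clinical Research Unit". At the first appointment, participants receive an information letter and may ask questions. Then: "When informed consent is given, a copy will be provided to the participant, and the study measurements will begin". Item 2 of the physiological measures reads: "After a fasting blood sample is taken (see above procedure), participants will be asked to drink a liquid containing glucose". A second sample follows at 120 minutes, and breakfast comes after that. The second appointment repeats the physiological measures.

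**Risk text.** Ethical Considerations says that the blood samples and the glucose test both require fasting, and names hunger and fatigue as possible effects. It adds that the drink may make some people nervous, and continues: "However, the drink is merely sweet, and there are no known risks from participating in a glucose tolerance test".

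**The concern.** For someone on glucose-lowering treatment, three matters call for an individual medical decision: whether to fast, what to do with the medicine that morning, and whether to take a glucose load. That decision has to come before the fast, so it has to be prompted at screening. The entry rule as written prompts nothing, and the sentence on the glucose drink gives staff no reason to ask. What is at stake is the safety of any such participant. The comparison between arms is not in question.

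**Working it through.** The plan states no figure on this point, so there is none to reproduce. The check is a count and a reading of the path from screening to test.

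**1. Criteria.** 3 inclusion + 2 exclusion = 5.

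| Criterion | Subject | Covers diabetes or its treatment? |
|---|---|---|
| Inclusion 1 | Short stress score, 8-16 | No |
| Inclusion 2 | Availability | No |
| Inclusion 3 | Swedish | No |
| Exclusion 1 | Recent yoga or meditation | No |
| Exclusion 2 | Physical limits on yoga postures | No |

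Result: 0 of 5. Exclusion 2 is the only health-related exclusion, and it concerns fitness for the postures.

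**2. Source population.** The Participants section recruits mainly from the Malmö Offspring Study, among people reporting chronic stress in the past year. Unit visitors and community members are also eligible. No health filter is stated for any source. The word diabetes appears in the available text only in the title of one cited paper.

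**3. Order of events.** Screening against the criteria → appointment → participant fasts and attends → letter, questions and consent → fasting sample → glucose drink → 120-minute sample → breakfast. No medical or medication history is described at any step. The contact at which the participant can ask questions comes after the fast has begun.

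**4. Exposure per affected person.** 1 fast and 1 load per visit × 2 visits = up to 2 fasts and 2 loads. No exemption is stated at either visit.

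**5. Comparison within the plan.** For injury during yoga, Ethical Considerations names the risk and points to an exclusion that limits it. For fasting and the glucose test, it names hunger, fatigue, nervousness and discomfort from venipuncture, ties no criterion to them, and then denies any known risk of the test.

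**6. What cannot be computed.** The documents give neither the number of eligible people with diabetes or on treatment nor any event rate. Neither enrolment of such people nor harm to them is estimated here.

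**The case against.** The strongest reply is that part of the screening path cannot be read. Letters go out before the call, the call conveys the content of Appendices 3 and 4:1, and in-person recruits hear the same. All of this precedes any fast, and such letters are a natural place for fasting or medication advice. The screening text also does not say that the interviewer asks nothing beyond the criteria. The documents do not say what health information the team already holds on Malmö Offspring Study members, who attend the same Unit. This stands: the available text is silent, and silence does not show that no check exists. A reader might infer that people with treated diabetes will in fact be tested without any medical decision; the documents do not support that.

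There are also general safeguards. Participants are told of the procedures and may decline. Licensed medical staff take the blood. The Unit has physicians and can refer to the Emergency Department, although that is stated for mental distress. The opportunity to ask questions before consent weakens the concern about the glucose load more than the concern about the fast, and it relies on the participant to speak up. None of these, as described, identifies an affected person before the fast. Feedback of glucose results comes after the test.

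The clinical premise is also not stated in the documents. It is ordinary clinical reasoning and is treated here as an assumption. The cover page carries an ethics approval number, but nothing shows what was considered on this point.

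**Conclusion.** The point holds within limits. None of the 5 entry criteria and no described screening step asks about known diabetes or glucose-lowering treatment. A person on such treatment therefore qualifies as the criteria are written, and would be asked for up to 2 fasts and 2 loads with no prior medical decision described in the available text. The unqualified risk sentence is a separate fault: whatever the letters contain, it remains in the protocol as it stands.

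The verdict assumes that fasting, medication and a glucose load need individual medical judgement in treated diabetes. Confidence is medium, because the letters are unseen and the number affected is unknown and could be zero.

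Two further inferences should be resisted. Multiplying the roughly 120 planned participants by two visits gives the whole trial's testing load, including everyone for whom no concern arises, so it does not measure this problem. Nor do the documents give grounds for claiming bias between arms or an effect on the primary stress outcome.

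**What to change.** 1. Add one question on known diabetes or glucose-lowering treatment to the telephone and in-person screen. Refer a positive answer to the Unit's physicians. They decide, before the appointment is scheduled and before randomisation, how fasting and medication are handled and whether the glucose test is done. The fasting decision is needed even if the test is dropped, because the blood samples require fasting too. If the test is not done, omit it at both visits under the same rule in all three arms, and keep the person for every other measure.
2. In Ethical Considerations, delete the clause denying known risks of the glucose test. State instead that people with known diabetes or glucose-lowering treatment are assessed by a Unit physician before fasting or testing. Do not replace it with a statement that the test is free of risk for everyone else; the documents give no basis for that either.

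The cost is one question in a contact that already takes place, a decision by physicians already on the Unit staff, and one edited sentence. The downside is possibly a few missing 120-minute glucose values, a number that the documents do not allow to be estimated.
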